Study conclusion						●	See Section 4.4 for details

Note: The double-line borders indicate the analyses which will be performed on all data (i.e., data that are as clean as possible) obtained up to these timepoints.

AE = Adverse event; AESI = Adverse event of specific interest; AF = Atrial fibrillation; CMI = Cell-mediated immunity; eCRF = electronic case report form; pIMDs = Potential immune-mediated diseases; RSV = Respiratory Syncytial Virus; SAE = Serious adverse event; SoC = Standard of care; WOCBP = Women of childbearing potential.

- is used to indicate a study procedure that requires documentation in the individual eCRF.
- is used to indicate a study procedure that does not require documentation in the individual eCRF.

^a Visit 2 is planned in the CMI subset of the study population (30% of the group population i.e., 38 participants in the group, at the designated CMI sites).

^b Vital signs, urine sample for pregnancy test and blood sampling for RSV neutralizing titers, CMI and CCI must be taken on the same day, prior to study intervention administration. If the study intervention administration is delayed by any reason, the vital signs and samples (both blood and urine) will need to be collected again on the day of study intervention administration, urine pregnancy test needs to be repeated, and the first blood sample will be destroyed.

^c Participants must bring their diary cards at this visit for review, and the same would be re-dispensed to them.

^d AF will be considered as AESI in this study and will be additionally reported in the AF follow-up questionnaire (electronic or paper) in eCRF. The collection of AF will be performed following the AE/SAE reporting periods. The reporting of non-serious AF will be performed according to the unsolicited AE reporting period. The reporting of AF meeting the SAE definition (serious AF) will be performed according to the SAE reporting period.

Under special circumstances, home visits may be conducted at the discretion of the investigator (Refer to Section 8 for details).

Table 4 Intervals between study visits for IC 1-dose group (RSV_IC_1)

Interval	Planned visit interval	Allowed interval range
Screening Visit → Visit 1	-7 days	-30 to -7 days
Visit 1 → Visit 2*	7 days	7 - 14 days
Visit 1 → Visit 3	30 days	30 - 60 days
Visit 3 → Visit 4	30 days	30 - 42 days
Visit 1 → Visit 5	180 days	180 - 210 days
Visit 1 → Visit 6	365 days	350 - 380 days

* Only in the CMI subset.

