Table 5 Intervals between study visits for IC 2-dose group (RSV_IC_2)

Interval	Planned visit interval	Allowed interval range
Screening Visit → Visit 1	-7 days	-30 to -7 days
Visit 1 → Visit 2*	7 days	7 - 14 days
Visit 1 → Visit 3	30 days	30 - 60 days
Visit 3 → Visit 4	30 days	30 - 42 days
Visit 3 → Visit 5	180 days	180 - 210 days
Visit 3 → Visit 6	365 days	350 - 380 days

* Only in the CMI subset.

Table 6 Intervals between study visits for healthy participant group (RSV_HA)

Interval	Planned visit interval	Allowed interval range
Visit 1 → Visit 2*	7 days	7 - 14 days
Visit 1 → Visit 3	30 days	30 - 60 days
Visit 3 → Visit 4	30 days	30 - 42 days
Visit 1 → Visit 5	180 days	180 - 210 days
Visit 1 → Visit 6	365 days	350 - 380 days

* Only in the CMI subset.

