
 To evaluate the CMI response following RSVPreF3 OA investigational vaccine administration in a subset of participants in all groups. 	
 CMI response expressed as group geometric mean of the frequency of RSVPreF3-specific CD4+ and/or CD8+ T cells expressing at least 2 activation markers including at least one cytokine among CD40L, 4-1BB, IL-2, TNF-α, IFN-γ, IL-13, and IL-17 at pre-study intervention administration, Visit 2*, Visit 3*, Visit 4*, Visit 5* and Visit 6*, in a subset of participants (renal and lung SOT patients (1-dose and 2-dose group), and healthy participants).
Secondary-Safety	

 To evaluate the safety and reactogenicity following RSVPreF3 OA investigational vaccine administration in all groups. 	
 Percentage of participants reporting each solicited administration site event with onset within 7 days post-study intervention administration (i.e., the day of vaccination and 6 subsequent days). Percentage of participants reporting each solicited systemic event with onset within 7 days post-study intervention administration (i.e., the day of vaccination and 6 subsequent days). Percentage of participants reporting unsolicited AEs within 30 days post-study intervention administration (i.e., the day of vaccination and 29 subsequent days).

Objectives	Endpoints and estimands
	
 Percentage of participants reporting SAEs after study intervention administration (Day 1) up to study end (Visit 6). Percentage of participants reporting pIMDs after study intervention administration (Day 1) up to study end (Visit 6). Percentage of participants reporting SAEs related to study intervention administration after study intervention administration (Day 1) up to study end (Visit 6). Percentage of participants reporting pIMDs related to study intervention administration after study intervention administration (Day 1) up to study end (Visit 6). Percentage of participants reporting fatal SAEs after study intervention administration (Day 1) up to study end (Visit 6). Percentage of participants reporting AESIs (specific to renal and lung SOT patients) after first study intervention administration (Day 1) up to study end (Visit 6).

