4. STUDY DESIGN

4.1. Overall design

The study design overview is presented in [Figure 1](#).

Experimental design: Phase 2b, randomized, multi-center, open-label study with three parallel groups (see [Figure 1](#)).

Study groups and Randomization and enrollment rules: Approximately 375 eligible participants will be enrolled in the study, under the following groups.

- Approximately 250 IC adults ≥ 18 YoA who received a renal or lung SOT, will be randomly assigned (1:1) to the following 2 IC groups (1 dose versus 2 doses; 125 participants each) at Visit 1 (Day 1). Each group may include approximately 65% renal transplant patients and approximately 20% lung transplant patients, and the remaining patients can be freely distributed across the 2 groups.
 - **RSV_IC_1 group:** IC patients receiving 1 dose of RSVPreF3 OA investigational vaccine at Visit 1 (Day 1).
 - **RSV_IC_2 group:** IC patients receiving 2 doses of RSVPreF3 OA investigational vaccine at Visit 1 (Day 1) and Visit 3 (Visit 1 + 30-60 days).
- Approximately 125 healthy adults ≥ 50 YoA (distributed among age categories of 50-59 YoA (30 %), 60-69 YoA (30%), ≥ 70 YoA (20%), and 20% to be freely distributed over the different age categories) will be assigned to the healthy participants group.
 - **RSV_HA group:** Healthy participants receiving 1 dose of RSVPreF3 OA investigational vaccine at Visit 1 (Day 1).

Primary completion date: Visit 4 (1 month after the last study intervention administration).

Duration of the study: The total duration of the study, per participant, will be approximately 13-15 months for the IC patients and 12 months for the healthy participants.

Type of study: self-contained.

Data collection: A standardized eCRF will be used. Solicited events will be collected as of the day of each study intervention administration and for 6 subsequent days. Unsolicited AEs, new concomitant medications/vaccinations will be collected as of the day of each study intervention administration and for 29 subsequent days. As of Day 30 following each study intervention administration, the details are collected in source documents prior to entering them in the eCRF until study end.

Safety monitoring: The study will be monitored by an IDMC as well as the project SRT (Refer Section 8.3.4 and Section 10.1.6).

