4.2. Scientific rationale for study design

RSV is associated with serious illness in OA and high-risk adults, including those who are immunocompromised that may lead to increased risk of RSV-LRTD. The efficacy of a single dose of the RSVPreF3 OA investigational vaccine in the prevention of RSV-LRTD in OA ≥ 60 YoA has been shown in the Phase 3 clinical study RSV OA=ADJ-006 (refer to IB).

Since the immune response in IC patients is often lower compared to healthy persons, the current study is designed as a Phase 2, open-label study to evaluate the immune response, safety, and reactogenicity of 1 versus 2 doses of RSVPreF3 OA investigational vaccine in

an IC population (renal and lung SOT patients) ≥ 18 YoA and additionally comparing it to 1 dose in healthy participants ≥ 50 YoA.

The inclusion of the 1-dose group in the SOT patient groups will provide more robust information and will help to make an informed decision on the need to use 1 dose versus 2 doses by comparing the immune response (in terms of GMT ratios in neutralization titers against RSV-A and RSV-B, as well as cell-mediated immunity) in the 1-dose group at Visit 3 and Visit 4 with the immune response in the 2-dose group at Visit 4.

In addition, a comparison on humoral and cell-mediated immunity at all timepoints up to 12 months post-last dose (including Month 6 and Month 12) between both groups of SOT patients as well as comparison to healthy participants will provide important information on waning of the immune response. In this study, the inclusion of a group of healthy adults ≥ 50 YoA will help to better elucidate the potential differences in immunogenicity and safety in the SOT patient groups versus healthy participants as of 50 YoA. Having head-to-head comparison with the healthy group will aid in the characterization of the immune response (both humoral and cell-mediated) of the IC population. Specifically for RSV, it is important that the healthy group is included in the same study since the primed status of the healthy adults and therefore the immune response to the vaccine, might differ between studies, as RSV seasonality can be different across countries/regions and years. Moreover, a head-to-head comparison with the healthy participants group will also enable further characterization of the reactogenicity of RSVPreF3 OA vaccine in IC population.

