9.3.2. Secondary endpoints/estimands analyses

Refer to Section 3 for the definition of secondary immunogenicity (humoral and CMI response) and safety endpoints. The immunogenicity analysis will be based on the PPS and safety analysis will be based on the ES.

For humoral immune response, the following analysis will be tabulated for each immunological assay (RSV-A and RSV-B neutralization titers):

- Percentage of participants above predefined threshold and GMT, with 95% CI, at pre-study intervention administration (Visit 1), Visit 2 (in a subset of participants), Visit 3, Visit 4, Visit 5, and Visit 6 in all groups.
- GMT ratio (RSV_HA group over RSV_IC group (pooled RSV_IC_1 and RSV_IC_2 group) with 95%CI, at Visit 2 (in a subset of participants) and Visit 3.
- GMT ratio (RSV_IC_2 group over RSV_IC_1 group) with 95% CI, at Visit 4, Visit 5, and Visit 6.
- GMT ratio (RSV_HA group over RSV_IC_1 group) with 95% CI, at Visit 4, Visit 5, and Visit 6.
- GMT ratio (RSV_HA group over RSV_IC_2 group) with 95%CI, at Visit 4, Visit 5, and Visit 6.
- MGI (RSV_IC group [pooled RSV_IC_1 and RSV_IC_2 group] and RSV_HA group) with 95% CI, at Visit 2 (in a subset of participants) over Visit 1, and at Visit 3 over Visit 1.

- MGI (RSV_IC_1, RSV_IC_2 and RSV_HA group) with 95% CI, at Visit 4, Visit 5 and Visit 6 over Visit 1.

The GMT ratios and their 95% CIs will be derived from an ANCOVA model on log10-transformed titers (details will be provided in the SAP).

The following analysis will be tabulated by group for CMI response in the CMI subset:

- Descriptive statistics (N, geometric mean, min, Q1, median, Q3, max) for the frequency of RSVPreF3-specific CD4+ and/or CD8+ T cells expressing at least 2 activation markers including at least one cytokine among CD40L, 4-1BB, IL-2, TNF- α , IFN- γ , IL-13, IL-17 at pre-study intervention administration (Visit 1), Visit 2, Visit 3, Visit 4, Visit 5, and Visit 6 in all groups.

Descriptive safety analysis by group will be summarized as follows:

- Percentage of participants reporting each solicited administration site event and solicited systemic event during a 7-day follow-up period (i.e., on the day of study intervention administration and 6 subsequent days) after each study intervention administration.

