- Percentage of participants reporting unsolicited AEs during a 30-day follow-up period (i.e., on the day of study intervention administration and 29 subsequent days) after each study intervention administration by MedDRA Primary System Organ Class (SOC), High Level Term (HLT) and Preferred Term (PT).
- Percentage of participants reporting SAEs from study intervention administration (Day 1) up to study end (Visit 6) by MedDRA Primary SOC, HLT and PT.
- Percentage of participants reporting pIMDs from study intervention administration (Day 1) up to study end (Visit 6) by MedDRA Primary SOC, HLT and PT.
- Percentage of participants reporting SAEs related to study intervention administration from study intervention administration (Day 1) up to study end (Visit 6) by MedDRA Primary SOC, HLT and PT.
- Percentage of participants reporting pIMDs related to study intervention administration from study intervention administration (Day 1) up to study end (Visit 6) by MedDRA Primary SOC, HLT and PT.
- Percentage of participants reporting fatal SAEs from study intervention administration (Day 1) up to study end (Visit 6) by MedDRA Primary SOC, HLT and PT.
- Percentage of participants reporting AESIs (specific to renal and lung SOT patients) from study intervention administration (Day 1) up to study end (Visit 6) by MedDRA Primary SOC, HLT and PT.

- Percentage of participants reporting demyelinating disorder during a 30-day follow-up period (i.e., on the day of study intervention administration and 29 subsequent days) after each study intervention administration by MedDRA Primary SOC, HLT and PT.
- Percentage of participants reporting demyelinating disorder SAE from study intervention administration (Day 1) up to study end (Visit 6) by MedDRA Primary SOC, HLT and PT.

Exact 95% CIs around percentages will be computed using the method of Clopper and Pearson [[Clopper](#), 1934].

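### Day 1-to-Visit 6 safety percentages cover 365 planned days in the 1-dose transplant arm and 395 in the 2-dose arm, so read side by side they slightly inflate the 2-dose arm

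*Protocol*

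**What the plan says.** Section 9.3.2 introduces the safety tables with "Descriptive safety analysis by group will be summarized as follows". The all-cause SAE item reads "Percentage of participants reporting SAEs from study intervention administration (Day 1) up to study end (Visit 6"). Fatal SAEs, pIMDs and transplant-specific AESIs have the same window there and in Table 7 of Section 3, where the AESI endpoint runs "after first study intervention administration (Day 1) up to study end (Visit 6"). Section 9.3.2 adds "Percentage of participants reporting demyelinating disorder SAE from study intervention administration (Day 1) up to study end (Visit 6"). Exact Clopper-Pearson 95% intervals are put around each percentage. Neither section states a common cut-off or a person-time denominator.

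The end of that window depends on the arm. In Table 4 (RSV_IC_1) and Table 6 (RSV_HA) the row is "Visit 1 → Visit 6", planned at 365 days with 350-380 allowed. In Table 5 (RSV_IC_2) the row is "Visit 3 → Visit 6", with the same figures but counted from the second-dose visit. That visit is itself planned 30 days after Visit 1, with 30-60 allowed.

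Section 4.2 says the study is designed to "evaluate the immune response, safety, and reactogenicity of 1 versus 2 doses of RSVPreF3 OA investigational vaccine". Section 4.1 gives a study duration of "approximately 13-15 months for the IC patients and 12 months for the healthy participants".

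**The concern.** RSV_IC_1 is the only randomised comparator for the safety of a second dose. In transplant recipients, SAEs, deaths and rejection episodes can accrue with time whether or not a second dose has any effect. If the same named percentage covers a month more in one randomised arm, its expected value is higher there for that reason alone, and the direction is known in advance: it counts against two doses. The tables are descriptive and will be compared by eye, so a small excess in RSV_IC_2 could be partly a product of the window.

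The point is confined to all-cause events between the two transplant arms. Events judged related to vaccination are not part of the sizes below: follow-up after the last dose is 365 planned days in both arms, so any effect on them is likely smaller.

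**Working it through.** **Inputs.** The visit intervals come from Tables 4 and 5, and 125 per transplant arm from Sections 4.1 and 9.5. The protocol gives no background rate for these events, so one-year risks p of 2%, 10%, 20% and 30% in RSV_IC_1 are assumptions. So are a constant hazard equal in both arms and complete follow-up.

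**1. Windows from Day 1 to Visit 6.**
- RSV_IC_1: 365 planned days, 350-380 allowed.
- RSV_IC_2: 30 + 365 = 395 planned; 30 + 350 = 380 to 60 + 380 = 440 allowed.
- Ratios: 395/365 = 1.082 at planned timing; 425/365 = 1.164 with dose 2 at day 60 and Visit 6 at its planned offset; 440/380 = 1.158 at the latest allowed visits in both arms.

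**2. Check against the stated duration.** With screening (7 planned, 7-30 allowed days) and 30.44 days per month:
- RSV_IC_2: 395 + 7 = 402 planned days = 13.2 months (387-470 days, 12.7-15.4 months). This fits the 13-15 months in Section 4.1.
- RSV_IC_1: 365 + 7 = 372 planned days = 12.2 months (357-410 days, 11.7-13.5 months). The planned value lies below that range.
- RSV_HA: 365/30.44 = 12.0 months, as stated.

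**3. Effect with no true difference.** Risk by day T is 1 - (1 - p)^(T/365). With q the RSV_IC_2 risk, the 95% half-width of the difference is 1.96 × sqrt[p(1-p)/125 + q(1-q)/125]. Example: p = 0.20 gives q = 1 - 0.80^(395/365) = 0.2145, an excess of 1.45 points against a half-width of 10.05 points, ratio 0.14.

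| One-year risk, RSV_IC_1 | RSV_IC_2, 395 days | Excess (points) | Half-width (points) | Ratio | RSV_IC_2, 425 days | Ratio |
|---|---|---|---|---|---|---|
| 2% | 2.16% | 0.2 | 3.54 | 0.05 | 2.32% | 0.09 |
| 10% | 10.78% | 0.8 | 7.56 | 0.10 | 11.55% | 0.20 |
| 20% | 21.45% | 1.5 | 10.05 | 0.14 | 22.88% | 0.28 |
| 30% | 32.02% | 2.0 | 11.46 | 0.18 | 33.99% | 0.35 |

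At the latest allowed visits in both arms (440 against 380 days) the excess is 0.3, 1.5, 2.9 and 3.9 points. In the extreme corner where every 1-dose participant ends at day 350 and every 2-dose participant at day 440, a 30% risk in RSV_IC_1 gives an excess of 6.1 points, still inside a half-width of 11.6.

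**4. What a reader would see.** With binomial counts, 125 per arm, 20% against 21.45%, the 2-dose count is higher, tied or lower with probability 58%, 6% and 36%. With equal windows at 20% the figures are 47%, 6% and 47%. About 12,200 per arm would be needed to detect this difference with 80% power.

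**5. Does equal follow-up remove it?** At p = 20%, expected first events are 25.0 over 112.0 person-years (365 days) and 26.8 over 120.2 (395 days). Both give 22.3 per 100 person-years. A percentage up to a common day is also equal in both arms when the hazards are equal, and does not need them to be constant.

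**The case against.** The case against is substantial, and most of it limits the importance of the point.

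- *It belongs in the SAP.* Section 9.3 calls itself a summary and leaves supportive analyses to the SAP, which is not at hand and may already hold a person-time table. If so, a cross-reference settles the matter. But the crude percentage and its arm-dependent window are fixed in the protocol itself, so the imbalance is in the plan as written and is more than an omitted detail.
- *Nothing in 9.3.2 is wrong.* Each percentage describes its own window correctly, and no safety difference or ratio is defined. For choosing between one and two doses, Section 4.2 specifies immune-response comparisons. This stands, and it confines the point to the side-by-side reading that the safety aim in Section 4.2 invites.
- *Balanced looks exist.* The 7-day and 30-day tables are per dose. Visit 4 is Visit 3 plus 30-42 days in both transplant arms, so the primary completion analysis has equal windows around the second dose. This also stands, but it does not balance the tables to Visit 6.
- *The effect is small and rests on assumptions.* True; ordinary dropout could offset a 30-day gap.

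A reader might infer that the last-dose anchor is a mistake. The documents do not support that: Section 4.2 plans follow-up to 12 months after the last dose. A reader might also infer that the protocol conceals the unequal follow-up behind one duration. It does not. The visit tables show the windows, and Table 11 and Section 8.2.1 give 12-15 months.

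**Conclusion.** The point holds as a minor one. The same safety percentage covers 365 planned days in RSV_IC_1 and 395 in RSV_IC_2 (8.2% more), which builds a small upward lean for the 2-dose arm into the only randomised safety comparison of one against two doses. For one-year risks of 2% to 30% the lean is about 0.2 to 2.0 points at planned timing, or 5% to 18% of the 95% half-width. If every second dose fell at day 60, it would reach 9% to 35%. These sizes depend on the assumed risks, a constant and equal hazard, and complete follow-up. The windows themselves come straight from the tables.

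It would be tempting to go further and call the safety comparison invalid, or to attribute any excess in the 2-dose arm to follow-up. Neither is supported. No test is planned, the artefact is below sampling error, and an excess well above these sizes could not be explained by the window. The primary endpoint and the sample size are unaffected.

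**What to change.** Keep the Day 1-to-Visit 6 percentages, the visit schedule and the last-dose anchor. In Section 9.3.2, state that comparisons of RSV_IC_1 with RSV_IC_2 on these all-cause events will also be shown over equal follow-up, with median follow-up per group, in one of two ways:

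- the percentage with a first event up to a common day counted from Day 1 that both arms reach, for example Day 350 (the earliest allowed Visit 6 in RSV_IC_1 is 350 days after Visit 1), with a Kaplan-Meier estimate to allow for early dropout; or
- participants with a first event per person-year, with a 95% CI.

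The common cut-off is the simpler choice, because it needs no constant-hazard summary.

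The cost is one extra set of tables from dates already collected, with no change to visits, data capture or sample size. Each option has a drawback. The common cut-off drops the last weeks of 2-dose follow-up from that comparison (395 - 350 = 45 days at planned timing). A person-time rate can dilute risk concentrated just after a dose, which the retained 30-day tables partly cover.

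As a separate editorial correction, reconcile the 13-15 months given for all transplant patients in Section 4.1 with the 12-15 months in Table 11 and Section 8.2.1, and with Tables 4 and 5. With screening, those tables give 12.2 planned months for RSV_IC_1 and 13.2 for RSV_IC_2.

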8.4.4.2. Atrial fibrillation (AF)

AEs of AF are considered as AESI in this study.

In the efficacy study (RSV OA=ADJ-006), at the time of safety analysis (data lock point [DLP]) of 30 April 2022, a numerical imbalance in events of AF was observed within 30 days post-vaccination, with 10 events of AF (among which 7 [0.1%] were serious) in the RSVPreF3 group versus 4 (among which 1 [<0.1%] was serious) in the placebo group. No imbalance was observed for serious events of AF reported within 6 months post-vaccination. To further characterize events of AF, AF will be considered as an AESI.

When there is enough evidence to make the above diagnosis, the AE must be reported as AESI. Symptoms, signs or conditions which might (or might not) represent AF, should be recorded and reported as AEs but not as AESI until the final or definitive diagnosis has been determined, and alternative diagnoses have been eliminated or shown to be less likely.

For each case of AF reported in the AE or SAE section in the eCRF, additional information will be collected in a specific 'AF follow-up questionnaire' eCRF screen.

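### The SAE, pIMD and rejection tables run from Day 1 to Visit 6, which dilutes any short-term excess after dose 2 and gives the two transplant arms windows of unequal length

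*Protocol*

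**What the plan says.** Protocol 4.1 sets the randomised comparison: "Approximately 250 IC adults ≥ 18 YoA who received a renal or lung SOT, will be randomly assigned (1:1") to one or two doses, 125 per arm. The arms part only when the second dose is given, since RSV_IC_2 consists of "IC patients receiving 2 doses of RSVPreF3 OA investigational vaccine at Visit 1 (Day 1) and Visit 3 (Visit 1 + 30-60 days").

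Table 7 in Section 3 defines the transplant endpoint as "Percentage of participants reporting AESIs (specific to renal and lung SOT patients) after first study intervention administration (Day 1) up to study end (Visit 6"). Section 9.3.2 repeats that window, listing "Percentage of participants reporting AESIs (specific to renal and lung SOT patients) from study intervention administration (Day 1) up to study end (Visit 6"), and applies it to the other events of interest: "Percentage of participants reporting SAEs from study intervention administration (Day 1) up to study end (Visit 6) by MedDRA Primary SOC, HLT and PT" and "Percentage of participants reporting pIMDs from study intervention administration (Day 1) up to study end (Visit 6) by MedDRA Primary SOC, HLT and PT". Related SAEs, fatal SAEs and related pIMDs are handled in the same way.

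Two listed summaries are tied to each dose over 30 days: unsolicited AEs and demyelinating disorders. Section 9.4.1 adds a primary completion analysis, run once data up to Visit 4 are available, with safety included.

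Tables 1 and 2 have SAEs, pIMDs and transplant AESIs recorded from Visit 1 through Visit 6 in both transplant arms. Tables 4 and 5 time Visit 6 at 350-380 days from Visit 1 in RSV_IC_1, but at 350-380 days from Visit 3 in RSV_IC_2.

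**The concern.** The randomised one-dose arm is the natural control for what the second dose does. The listed windows make poor use of it in three ways:

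- Events in the first 30-60 days are counted although the arms have not yet been treated differently.
- A cluster shortly after dose 2 is mixed with about a year of background rejection and hospitalisation.
- The two-dose arm is observed for longer, so it collects more background events even if the second dose does nothing.

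This matters because Section 2.3.1 names allograft rejection as a theoretical risk of adjuvanted vaccination in transplant recipients, and Section 4.2 says the one-dose arm is there to inform the choice between one and two doses. Section 8.4.4.2 also shows that window length can change the picture. In the efficacy study serious AF was 7 versus 1 within 30 days of vaccination, yet "No imbalance was observed for serious events of AF reported within 6 months post-vaccination".

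**Working it through.** **Inputs from the protocol**
- 125 per arm (4.1 and 9.5). This agrees with 100 evaluable and 20% attrition: 100 / (1 - 0.20) = 125.
- Visit 3 is 30-60 days after Visit 1 (planned 30). Visit 4 is 30-42 days after Visit 3 (planned 30). Visit 6 is as in Tables 4 and 5.
- The protocol states no rejection, SAE or pIMD rate and no safety power, so there is no figure of its own to reproduce.

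**Window lengths, Day 1 to Visit 6**
- RSV_IC_1: 350-380 days (planned 365).
- RSV_IC_2: 30 + 350 = 380 to 60 + 380 = 440 days (planned 30 + 365 = 395).
- At the same Visit 6 offset the difference is the Visit 1 to Visit 3 interval, 30-60 days.
- The 30 days after dose 2 are 30/395, about 8% of the planned RSV_IC_2 window.

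**Effect of unequal length with no vaccine effect**

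Take an assumed annual risk a with a constant hazard, λ = -ln(1 - a)/365. The extra risk from k more days is exp(-365λ) - exp(-(365 + k)λ).

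| Assumed background per year | 30 extra days | 60 extra days |
|---|---|---|
| 2% | 0.16 points | 0.32 points |
| 5% | 0.40 | 0.80 |
| 8% | 0.63 | 1.25 |
| 10% | 0.78 | 1.55 |

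**Dilution of a short-term excess**

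Assume 8% a year and a true excess e within 30 days of dose 2. Over d days, q = 1 - exp(-λd) in RSV_IC_1 and p = 1 - (1 - q)(1 - e) in RSV_IC_2. With λ = -ln(0.92)/365 = 0.000228, q is 0.0068 at 30 days, 0.0136 at 60 days and 0.0800 at 365 days. Both arms are given the same length here, so the inequality above does not enter. Power is for a one-sided 5% Fisher exact test, summed over the two binomial distributions. It serves only as a yardstick, because the plan tests nothing.

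| Window | Expected participants, e = 3 points | Risk ratio | Difference | Power, e = 3 | Power, e = 5 |
|---|---|---|---|---|---|
| 30 days from Visit 3 | 0.9 vs 4.6 | 5.4 | 3.0 points | 0.28 | 0.61 |
| Day 1 to Day 60 (planned Visit 4) | 1.7 vs 5.4 | 3.2 | 3.0 | 0.24 | 0.52 |
| One year from Day 1 | 10.0 vs 13.5 | 1.35 | 2.8 | 0.13 | 0.25 |

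The ordering for e = 5 holds at other backgrounds: 0.66, 0.59 and 0.32 at 5% a year, and 0.56, 0.46 and 0.20 at 12%. For e = 2 at 8% the power is 0.12, 0.12 and 0.08, so no window helps much.

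**Does another listed table give the comparison?**
- Unsolicited AEs, 30 days after each dose: serious events are included (10.3.4), so events after dose 2 should appear. RSV_IC_1 has no second dose, and Table 1 schedules its unsolicited AEs only at Visits 1 to 3, so there is no concurrent column.
- Demyelinating disorders, 30 days after each dose: a narrow set of events with the same missing column.
- Primary completion analysis: the schedule footnotes describe data obtained up to the timepoint, whereas 9.4.1 refers to all safety data available. Only a cut at Visit 4 gives something like the middle row above, and it would still start at Day 1.

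**The case against.** The strongest reply is that nothing stated is wrong. Section 9.3 calls itself a summary and leaves supportive analyses to the SAP, which is not shown. Safety is descriptive, an IDMC with transplant expertise reviews the data, and rejection is reportable within 24 hours of determination, with its start date recorded. Much of this stands, and it limits the weight of the point. It does not remove it, because Table 7 and 9.3.2 themselves fix the windows, including their unequal length.

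A reader might infer that Day 1 to Visit 6 is the only view of these events and that a second-dose signal would be hidden. The documents do not support that. Serious events after dose 2 also fall in the per-dose unsolicited AE table, and a Visit 4 cut, if applied, recovers much of the gain (power 0.52 against 0.61 for a 5-point excess). Over a year the absolute difference hardly shrinks (2.8 against 3.0 points). The excess is diluted by background noise but is not removed.

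Nor does the AF history prove the case. The protocol does not say the 30-day imbalance was causal, and a difference seen at 30 days but not at 6 months also fits chance.

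Two cautions apply to any remedy. A comparison from Visit 3 to each arm's own Visit 6 would again give RSV_IC_2 about 30-60 more days. Restricting to participants still present at Visit 3 conditions on something that happens after open-label randomisation, so losses before Visit 3 must be shown by arm.

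**Conclusion.** The point holds as a weakness in a stated analysis. The listed SAE, pIMD and transplant-AESI windows begin 30-60 days before the arms differ, last about a year, and are about 30-60 days longer in the two-dose arm. No listed table sets the two arms side by side from Visit 3, although both supply the data.

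The two consequences pull in different directions: background dilutes a real short-term excess, while the longer window slightly inflates the RSV_IC_2 percentage when there is none. The sizes rest on assumed background rates, an assumed excess confined to 30 days and a constant hazard. With 125 per arm, an excess of 2 or 3 points would be hard to distinguish from chance in any window. What is gained is a clearer descriptive comparison.

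**What to change.** Keep the existing tables and make two additions to 9.3.2:

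1. For RSV_IC_1 and RSV_IC_2 side by side, give the percentage (exact 95% CI) with onset of a transplant AESI, an SAE or a pIMD in the 30 days starting on the Visit 3 date. Use the same start rule in both arms and include participants still in follow-up at Visit 3. Show by arm the number who did not reach Visit 3.
2. For the long window, compare the two transplant arms over equal follow-up, for example by truncating both at the same number of days from Day 1 or from Visit 3, or report exposure-adjusted rates.

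It would also help to say in 9.4.1 whether the safety data in the primary completion analysis stop at each participant's Visit 4.

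The cost is a few more tables from data already collected, with no change to conduct. Events will be few and the intervals wide, so the tables should be labelled descriptive.
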